### 2.1.2 Data Collection

Data collection will occur at three time points: at baseline and again at 6 and 12 months of follow-up. During each assessment, participants will complete self-administered questionnaires on tablets or smartphones via the Qualtrics platform. For individuals assigned to the STOS group, HIV self-testing outcomes will be documented by a trained counselor and stored in an encrypted file with restricted access. Only the Principal Investigator (PI) and the Study Statistician will be authorized to view these data to maintain strict confidentiality.

All study data will be housed on secure institutional servers in encrypted, password-protected formats to ensure robust data security.

### 2.1.3 Retention and Engagement Strategies

To ensure sustained participation throughout the follow-up period, the research team will implement continuous engagement measures using multiple digital communication channels, including the Zalo application, SMS, telephone calls, and support from community peer leaders. Participants will be contacted regularly to receive project updates, appointment reminders, and encouragement to take part in each data-collection round. Ongoing assistance will also be provided to help maintain participants' motivation and consistency in completing questionnaires. For the STOS group, follow-up communication will additionally ensure that participants receive their self-testing kits. These combined strategies are expected to achieve follow-up retention rates exceeding 80% at each assessment point.

## 2.2 Eligibility criteria

### **Inclusion Criteria:**

- Aged between 16 and 29 years
- Have been residing in Ho Chi Minh City for more than 6 months
- Assigned male at birth or intersex
- Self-identify as men who have sex with men (MSM), Homosexual, bisexual, or male (straight)
- Have engaged in anal sex (insertive or receptive) with a male partner within the past 6 months
- Willing and able to provide informed consent to participate in the study

### **Exclusion Criteria:**

- Aged  $\leq 15$  years or  $\geq 30$  years
- Have been residing in Ho Chi Minh City for less than 6 months or do not currently live in Ho Chi Minh City.
- Assigned female at birth
- Self-identify as a woman, transgender woman, or transfeminine individual
- Unwilling to participate in follow-up activities associated with the study

## 2.3 Consent

### 2.3.1 Consent Procedures

All participants will provide informed consent by clicking "accept button" at the time they begin the online survey. For participants under 18 years of age, a waiver of parental consent will be obtained from the ethics committee to protect them from the potential risk of unintentional

disclosure of their sexual orientation or HIV status. Before joining the study, participants will receive a study information sheet explaining the research objectives and procedures. This document will appear immediately before the consent question in the online survey, allowing participants to review the study details before providing consent. After completing the survey, participants who are interested in joining the STOS intervention will be introduced to additional information, as follows: Participants will be informed that the study involves an online HIV self-testing intervention and that they may be randomly assigned to one of two testing approaches.

The first approach involves receiving an HIV home self-testing kit, with real-time guidance and support from trained staff via video calls and instructional videos. The second approach involves receiving information about free HIV testing services available at public hospitals, where participants can go for testing independently. If selected for participation, study staff will contact participants using the contact information provided to explain further details and confirm their willingness to take part. For those who are randomly assigned to the STOS group, multiple formats will be used to ensure a full understanding of study procedures. These include printed materials, instructional videos (e.g., how to perform HIV self-testing), and verbal explanations provided by trained counsellor. Participants will be encouraged to ask questions about any aspect of the study, including the survey process, HIV self-testing procedures, and their right to withdraw from the study at any time without penalty or loss of benefits. Informed consent will be obtained only after participants demonstrate clear understanding and express their willingness to participate voluntarily. At each follow-up round, field staff will reassess participants' understanding and verbally reconfirm consent before administering questionnaires or conducting STOS sessions, to ensure that participants remain fully informed and voluntarily engaged throughout the longitudinal study

### 2.3.2 Withdrawal/discontinuation criteria

Participants could withdraw from the study at any time and for any reason. Withdrawal did not affect the compensation they had already received or their access to HIV-related services. Common reasons for discontinuation included being unreachable, or unwillingness to continue participation.

## 2.4 Data analysis

Both descriptive and inferential statistical methods will be employed to evaluate the effectiveness of the STOS intervention throughout the study period. Analyses will compare the STOS intervention group and the control group across demographic variables, behavioral measures, and health-related outcomes associated with HIV infection.

### 2.4.1 Descriptive Analyses

Baseline characteristics of participants, including demographic, behavioral, and health-related information, will be summarized using descriptive statistics, stratified by study group (intervention vs. control) to assess baseline differences between the two groups and changes over time. Categorical variables will be presented as frequencies and percentages, while continuous variables will be summarized using means and standard deviations (mean  $\pm$  SD) or medians with interquartile ranges (IQR: 25th–75th percentile), depending on the data distribution.

#### 2.4.2 Primary and Secondary Outcome Analyses

To evaluate the effects of the STOS intervention, two groups will be compared: the STOS group, who receive an HIV self-testing kit and complete the online questionnaires, and the control group, who complete the questionnaires only. The primary outcomes are the rate of HIV testing uptake and the rate of new HIV infections during the study period. The secondary outcomes include changes in sexual behaviors, mental health, and other psychosocial indicators over time. To assess the effects of the intervention across time points, Generalized Estimating Equations (GEE) models will be applied, using a log link function for rate outcomes and an identity link function for continuous outcomes. The models will include variables for study arm (STOS vs. control), time (follow-up round), and their interaction term (arm  $\times$  time) to estimate longitudinal intervention effects. Robust standard errors will be used to account for within-subject correlation due to repeated measures. The results will be presented as Rate Ratios (RRs or Incidence Rate Ratios, IRRs) with 95% confidence intervals (CIs) and p-values to indicate the magnitude and statistical significance of the observed effects.

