### 3. Study Objectives and Endpoints

#### 3.1 Primary Objective

To evaluate the effectiveness of the STOS intervention in increasing access to and uptake of HIV testing among young men who have sex with men (YMSM).

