#### 3.2 Secondary Objectives

- To evaluate the effect of the intervention on reducing the incidence of HIV infection.
- To evaluate the effect of the intervention on reducing sexual risk behaviors (e.g., condomless anal intercourse with male partners).
- To evaluate the effect of the intervention on reducing health-related risk behaviors, including mental health problems (depression and suicidal risk) and substance use.

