#### 3.3 Primary Outcome

- **HIV testing uptake:**

Proportion of participants who report having tested for HIV at least once within a 6-month period, based on STOS testing records and self-reported survey data.

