#### 3.4 Secondary Outcomes

- **HIV incidence:**

Number of new HIV infections per 100 person-years, based on STOS testing results and self-reported data during follow-up.

- **Sexual risk behavior:**

Proportion of participants reporting condomless anal intercourse with male partners during the past 6 months, measured through self-reported survey data.

- **Health-related risk behaviors (mental health and substance use):**

Proportion of participants reporting mental health problems (e.g., depressive symptoms, suicidal risk) and frequency of substance use during the past 6 months, based on self-reported survey data.

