### 6.3 Multiple Comparisons and p-value Adjustment

For secondary outcomes and subgroup analyses involving several statistical tests, adjustments for multiple comparisons will be applied as appropriate. Methods such as Bonferroni correction or false discovery rate (FDR) procedures will be considered to control the risk of type I error.

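### The protocol names two primary outcomes and the SAP names one; the second, new HIV infections, cannot support a primary claim at this size.

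*Combined protocol and SAP*

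**What the plan says.** Protocol 2.4.2 is explicit: "The primary outcomes are the rate of HIV testing uptake and the rate of new HIV infections during the study period". Its next sentence gives the secondaries and leaves infection out: "The secondary outcomes include changes in sexual behaviors, mental health, and other psychosocial indicators over time".

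The SAP sets a different hierarchy:

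- SAP 3.1, the only primary objective: "To evaluate the effectiveness of the STOS intervention in increasing access to and uptake of HIV testing".
- SAP 3.3, the only primary outcome: "Proportion of participants who report having tested for HIV at least once within a 6-month period".
- SAP 3.2, among the secondary objectives: "To evaluate the effect of the intervention on reducing the incidence of HIV infection".
- SAP 3.4, among the secondary outcomes: "Number of new HIV infections per 100 person-years, based on STOS testing results and self-reported data during follow-up".

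On multiplicity, protocol 2.4.3 says only that p-value adjustment will be considered when several comparisons are made, with subgroups and secondary outcomes as examples. SAP 6.3 is narrower: "For secondary outcomes and subgroup analyses involving several statistical tests, adjustments for multiple comparisons will be applied as appropriate". Neither document states alpha, sidedness, or whether success in the protocol's sense needs one primary or both. Neither says which document governs if they differ.

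**The concern.** The outcome on which the trial will be judged depends on which document the reader opens. Under the protocol, an infection result is a primary finding with no stated alpha split. Under the SAP, it is a secondary finding open to multiplicity adjustment. If this is not settled before analysis, the hierarchy could be chosen after the data are seen.

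The two outcomes also differ greatly in how much the trial can say about them. Every participant contributes to uptake. New infections in 100 people over 12 months will be a handful at most, yet protocol 2.4.2 plans a log-link GEE with an arm-by-time interaction, rate ratios and p-values. With so few events over two follow-up rounds, empty cells are likely and the interaction may not be estimable.

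**Working it through.** **Inputs**

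- 50 participants per arm followed for 12 months (protocol 2): at most 50 person-years per arm.
- Retention expected above 80% (protocol 2.1.3): 40 person-years per arm as the low case.
- Incidence 5.8% among young MSM in Hanoi (protocol 1.1). No time unit is given and the trial is in Ho Chi Minh City. I read it as 5.8 per 100 person-years and also run 2 and 10; all three are assumptions.
- Two-sided alpha of 0.05, assumed because the protocol plans 95% intervals.

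The sample size of 100 cannot be reproduced, because no power, effect size or control rate is given.

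**Error rate with two primaries**

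- Either suffices, both tests at full size, independent: 1 − 0.95² = 0.0975. Without independence the bound is 0.05 + 0.05 = 0.10.
- Either suffices, incidence tested exactly: with 2.9 expected infections in each arm, the exact test's true size is 1.2%. Then 1 − 0.95 × (1 − 0.0117) = 0.061. The same sum gives 5.0% at 2 per 100 person-years and 7.1% at 10.
- Both required: at most 0.05, with overall power capped by the incidence test.
- The SAP's single primary: 0.05.

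**Expected infections**

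Control arm: 0.058 × 50 = 2.9 (0.058 × 40 = 2.3 in the low case). If STOS halved the rate, the total over both arms would be 2.9 + 1.45 = 4.35.

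**Power for incidence**

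The test is an exact conditional binomial test, averaged over Poisson counts. It stands in for the planned GEE, which is unreliable with so few events. A 5 v 0 split gives p = 2 × 0.5⁵ = 0.0625 and a 6 v 0 split gives 2 × 0.5⁶ = 0.031. Significance therefore needs at least 6 v 0. If STOS prevented every infection, power would be the probability of 6 or more control infections.

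| Assumed rate per 100 person-years | Person-years per arm | Expected control infections | Power, rate halved | Power, all prevented |
|---|---|---|---|---|
| 2 | 50 | 1.0 | 0.04% | 0.06% |
| 5.8 | 50 | 2.9 | 2.1% | 7.4% |
| 5.8 | 40 | 2.3 | 1.1% | 3.1% |
| 10 | 50 | 5.0 | 6.9% | 38% |

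A less conservative approximation (Schoenfeld) gives 11% for a halved rate at 5.8 with 50 person-years per arm, and 16% at 10. By the same method, 80% power for a halved rate needs 66 events. At the average rate over both arms, 0.058 × 0.75 = 0.0435, that is 66 / 0.0435 ≈ 1,517 person-years, against at most 100 available.

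**Ascertainment**

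SAP 5.2 combines the questionnaires from all participants with self-test results from the STOS arm only. Control infections therefore rest on self-report. An intervention that raises testing can also find more infections, so the rate ratio could mislead in direction at any sample size.

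**The case against.** The strongest defence is that this is a pilot, that Aim 3 concerns feasibility and acceptability, and that a pilot need not be powered. That stands: low power alone is not an error here. It does not excuse two different primary hierarchies, or naming as primary an outcome on which the trial carries so little information.

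Four stronger readings are tempting, and the documents do not support them.

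- A reader might infer that the protocol's multiplicity section excludes primaries, so that each is certain to be tested at 5%. Protocol 2.4.3 gives secondary outcomes and subgroups only as examples. Only SAP 6.3 is confined to them. What can be said is that the protocol has no explicit rule for two primaries.
- A reader might take 9.75% as the error rate, or as its ceiling. It needs full-size tests, independence and a rule that either outcome suffices. Nor does it belong beside the exact power figures, because the exact test gives about 6%.
- A reader might conclude that even complete prevention of infection would go undetected. That holds at 5.8 per 100 person-years (7%), but at 10 the power is 38%. Only the result for a halved rate holds across the whole range tried.
- A reader might say the SAP breaks its own promise of alignment. SAP 1.1 refers to the registered protocol, and the registry record cannot be checked here. What can be shown is that the SAP differs from the protocol text supplied with it.

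The inconsistency could also be removed by keeping both primaries with a stated success rule and an alpha split. At 0.025 each, family-wise error is 1 − 0.975² = 0.049. The detectable uptake difference at 80% power with 50 per arm rises from about 25–28 to about 27–30.5 percentage points, for assumed control uptake of 23.5% to 60%. The split would still leave incidence unanswerable.

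**Conclusion.** The point holds and should be settled before analysis. The two documents disagree, in current text, on whether HIV infection is a primary outcome, and nothing in either resolves it.

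The effect on the error rate depends on rules the documents do not give: from at most 5% if both primaries must succeed, through about 6%, to 9.75% (bound 10%) if either suffices.

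The conclusion that incidence cannot carry a primary claim is firmer. Exact power for a halved rate is about 2% at 5.8 per 100 person-years, and it stays between less than 0.1% and about 7% for assumed rates from 2 to 10. This rests on at most 50 person-years per arm, a two-sided 5% level, and an exact test in place of the planned model. Unequal ascertainment between arms is a separate reason, and it does not depend on those assumptions.

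**What to change.** Amend protocol 2.4.2 so that HIV testing uptake is the sole primary outcome, in line with SAP 3.1 and 3.3, and move new HIV infections to the secondary outcomes. In both documents, report incidence descriptively: infections and person-years per arm, exact 95% confidence intervals, and no test of effectiveness. Add a note that test records are merged for the STOS arm only, so the arms are not ascertained alike. Check the registry entry against the amended hierarchy.

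The cost is a short protocol amendment, a reporting line in the SAP, and any ethics or registry update that follows. Recruitment and data collection do not change, and little usable inference is lost, because incidence could not support a claim at this size.

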#### 2.4.3 Multiple Comparisons and p-value Adjustment

When multiple comparisons are made, such as in subgroup analyses or secondary outcomes, adjustments to p-values will be considered to control for the risk of type I error. Methods such as Bonferroni correction or false discovery rate (FDR) adjustment will be applied as appropriate.

#### 2.4.4 Statistical Software

All data analyses will be conducted using STATA version 18.0, which is the primary statistical software used by the research team for data management, descriptive analyses, regression modeling, and longitudinal data analysis.

## 2.5 Assessment and management of risk

This study will be conducted as a low-risk observational cohort study. However, certain items in the questionnaire, such as those related to sexual behavior or HIV status, may be considered sensitive. To minimize potential risks, several protective measures will be implemented. All data will be collected anonymously and stored securely using an encrypted system with restricted access, ensuring that no personally identifiable information is recorded.

Participants will be informed of their right to skip any question they find uncomfortable and their right to withdraw from the study at any time without any negative consequences. Additionally, counsellor will provide continuous support by explaining study procedures and addressing participants' questions throughout the study period. If necessary, participants will be referred to mental health or HIV-related services for appropriate care.

In cases where participants are found to be HIV positive, they will receive preliminary counseling and be referred to appropriate healthcare facilities for further testing and treatment in accordance with the Ministry of Public Health guidelines.

A Data and Safety Monitoring Board (DSMB) will also be established to oversee the project's risk management strategies, monitor participant safety and well-being, and ensure continuous ethical compliance. The DSMB will operate independently to review study procedures and provide recommendations to the research team regarding any necessary protocol adjustments to maintain ethical and safety standards throughout the study.

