## 2. Study design and methods of data collection

This study aims to evaluate the effectiveness of the HIV self-testing with online supervision (STOS) intervention, which includes the introduction of a HIV rapid diagnostic antibody/antigen-based self-testing conducted with the support of a trained counsellor via video conferencing, among young men who have sex with men (YMSM) aged 16–29 years.

The study employs a pilot randomized controlled trial (RCT) design with two groups: an intervention group (STOS) and a control group. The total sample size is 100 participants (50 per group). The follow-up period spans 12 months, with data collected at three time points: baseline, 6 months, and 12 months.

Data collection includes self-administered online questionnaires completed through the Qualtrics platform. For participants in the intervention group, the study involves the implementation of real-time online supervised HIV self-testing conducted by a trained counsellor through video conferencing.

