## 2.1 Procedures

### 2.1.1 Recruitment and Enrollment

Participant recruitment will be conducted over a one-year period, using a combination of online and offline outreach strategies to reach the target population of young men who have sex with men (YMSM) in Ho Chi Minh City.

For the online cross-sectional survey, recruitment will primarily be conducted through online platforms, including Google advertisements, Facebook, the CARMAH fan page, CARMAH networks, other MSM community networks, and youth networks in Ho Chi Minh City (such as university and high school students). To encourage participation, each respondent will receive a mobile top-up e-voucher valued at 50,000 VND (approximately 2 USD), delivered via SMS.

Individuals interested in participating will complete an online eligibility screening form. Those who meet the inclusion criteria will receive detailed study information and proceed with the initial electronic consent (e-consent). After completing the survey, if an individual is found to be HIV-positive, they will not be invited to participate in the pilot study.

For the pilot study, a total of 100 Vietnamese YMSM will be recruited and followed for 12 months. Participants will be randomly assigned into two groups of 50 each:

- The intervention group, which will receive the HIV self-testing with online supervision (STOS) intervention; and
- The control group, which will refer to the standard of care, consisting of a voucher for venue-based HIV testing.

The STOS program begins when a counsellor contacts eligible participants via the Zalo communication platform. After confirming eligibility, the counsellor obtains verbal informed consent and schedules an appointment for the HIV self-testing with online supervision (STOS) session.

Once the appointment is confirmed, HIV self-testing kits are delivered to participants through Be Delivery service. Before the testing session, participants receive a link to an instructional YouTube video developed by CARMAH and Mahidol University, which demonstrates the correct procedure for performing the HIV self-test.

During the scheduled session, the counsellor provides pre-test counselling and real-time supervision via video conferencing as participants perform the self-test. This process ensures proper use of the test kit, supports accurate interpretation of results, and maintains participant confidentiality throughout the HIV self-testing process.

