## 2.7 Recording and reporting of risk events and incidents

If an adverse or risk-related event occurs during the study, the research team will systematically document and review the incident. Key information, including the type of event, the time it occurred, the individuals involved, and any immediate actions taken, will be recorded.

The research team will evaluate the seriousness of the incident and determine the appropriate follow-up steps. Any event deemed serious or potentially compromising participant safety will be promptly reported to the Data and Safety Monitoring Board (DSMB) for independent assessment and recommendations. These incidents will also be submitted to the Institutional Review Board (IRB) within the required reporting window in accordance with ethical guidelines.

Clear procedures are in place to ensure that all incidents are handled in a timely, transparent, and appropriate manner. All incident documentation will be securely stored and treated as confidential. Participants may also communicate any concerns or discomfort to the research team through the confidential communication channels routinely used in the study, including Zalo and telephone contact.

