### 1.2 Background and Significance of the Study

This study aims to evaluate the effectiveness of the STOS intervention in:

- Increasing the frequency of HIV testing (at least once every six months)
- Reducing sexual risk behaviors

The study is conducted as a pilot randomized controlled trial (pilot RCT) using a longitudinal cohort design among young men who have sex with men (YMSM Cohort, N = 100) residing in Ho Chi Minh City, Vietnam, with participants randomized into two groups: the STOS intervention group and the control group.

Given that YMSM in Ho Chi Minh City, Vietnam continue to have low rates of HIV testing, a high burden of HIV, and face structural and behavioral barriers to accessing healthcare services, this study is of significant public health importance and holds meaningful implications for national HIV policy development and prevention programming.

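### The risk section labels the randomised trial observational and names only questionnaire sensitivity; apart from mental health, no harm measure is specified, and events are captured only when they come to notice

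*Combined protocol and SAP*

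**What the plan says.** Protocol section 2.5 opens its account of risk with the sentence "This study will be conducted as a low-risk observational cohort study". The one source of risk it then names is that "certain items in the questionnaire, such as those related to sexual behavior or HIV status, may be considered sensitive". It goes on to provide for secure data, freedom to skip questions, referral, counselling for men found HIV positive, and a DSMB.

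Elsewhere the design is different. Protocol section 2 says: "The study employs a pilot randomized controlled trial (RCT) design with two groups: an intervention group (STOS) and a control group". SAP section 1.2 says: "The study is conducted as a pilot randomized controlled trial (pilot RCT) using a longitudinal cohort design". Under protocol section 2.1.1, "HIV self-testing kits are delivered to participants through Be Delivery service", and a counsellor then supervises the test by video. Section 2.1.3 lists the contact channels used to keep men in the study: the Zalo application, "SMS, telephone calls, and support from community peer leaders".

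Section 2.3.1 justifies the waiver of parental consent for participants under 18 by the risk of unintentional "disclosure of their sexual orientation or HIV status".

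Section 2.7 sets out what the team does once an adverse or risk-related event has occurred, and adds: "Participants may also communicate any concerns or discomfort to the research team". SAP sections 3.2 to 3.4 list HIV testing, HIV incidence, sexual risk behaviour, mental health (depressive symptoms and suicidal risk) and substance use. They list no safety outcome.

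**The concern.** The risk statement rests on a design that this trial does not have. An observational study assigns nothing; this one assigns half its participants to a delivered kit and a supervised test. Because 2.5 discusses only the questionnaire, the risks that the assigned procedures might bring are not discussed: a parcel, message or call seen by someone else, or pressure to test or to show a result.

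The second gap is in how events reach the record. Section 2.7 is triggered by an event that someone has already noticed or volunteered. No scheduled question, list of foreseeable harms or tabulation by arm is specified. Few or no recorded events could then reflect little reporting as easily as little harm. Protocol section 5 foresees scale-up, and a pilot is the natural place to learn whether delivery and contact expose participants.

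**Working it through.** The plan gives no expected harm rate and no figure to reproduce, so most of this check compares the text.

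**1. The design label.** Protocol sections 2 and 2.1.1 and SAP sections 1.2 and 2 all describe random allocation to two groups of 50. The SAP also speaks of a longitudinal cohort, but in the same sentence as the randomised design, and it never says observational. Section 2.5 stands alone.

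**2. Trial procedures against the risk section.**

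| Procedure | Where described | Risk discussed in 2.5? |
|---|---|---|
| Online questionnaire | 2.1.2 | Yes, as sensitive items |
| HIV-positive result | 2.5 | Counselling and referral provided; no risk described |
| Couriered kit | 2.1.1 | No |
| Video session | 2.1.1 | No |
| Zalo, SMS, calls, peer leaders | 2.1.3 | No |

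**3. Identifiers.** Section 2.5 offers as a safeguard that nothing identifying a person is recorded. Section 2.6 links records across rounds by nickname and phone number. The two statements need reconciling, because this safeguard bears directly on disclosure.

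**4. What is asked and what is not.** Section 2.1.2 schedules questionnaires at baseline, 6 and 12 months for all participants, and SAP section 3.4 includes depressive symptoms and suicidal risk. So mental health is asked about in both arms, as an effectiveness outcome. No measure of disclosure, pressure or mistreatment is specified. The questionnaire itself is not in the documents.

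**5. Illustration of what capture does.** From the documents: n = 50 per arm, and retention expected to exceed 80%, hence about 0.80 × 50 = 40 men asked. Assumed: true risk p, and fraction c of events that are volunteered.

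P(at least one report) = 1 − (1 − p × c)^n

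With p = 5%:
- everyone asked and answering (c = 1, n = 50): 1 − 0.95^50 = 92.3%
- 40 men asked and answering: 1 − 0.95^40 = 87.1%
- volunteered, c = 10%, n = 50: 1 − 0.995^50 = 22.2%
- volunteered, c = 25%: 1 − 0.9875^50 = 46.7%
- volunteered, c = 50%: 1 − 0.975^50 = 71.8%

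At other true risks, with all 50 asked, the chance is 63.6% for p = 2% and 99.5% for p = 10%.

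If everyone asked reports no event, the one-sided 95% upper limit is 1 − 0.05^(1/n): 5.8% for n = 50 and 7.2% for n = 40. With volunteered reports no such limit can be given, because c is unknown.

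**6. Reporting by arm.** STOS men have counsellor sessions (2.1.1) and follow-up about kits (2.1.3) that controls do not. Take a harm with the same assumed risk of 10% in each arm, or 50 × 0.10 = 5 events per arm. If 50% were volunteered in STOS and 10% in control (both assumed), the record would show 5 × 0.50 = 2.5 against 5 × 0.10 = 0.5 events on average. This shows what unequal reporting could do. It does not show that reporting is unequal.

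**The case against.** The strongest reply is that a safety system exists. Section 2.5 gives the DSMB the task of watching participant safety and well-being. Section 4 has it review safety reports and risk events at set intervals, and has internal monitoring check confidentiality. Section 2.7 sends serious events to the DSMB and the IRB. All of this stands; the gap is in what reaches that system.

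Several stronger readings are tempting and are not supported:

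- *Harms are never asked about in either arm.* Depression and suicidal risk are surveyed in both arms. For other harms one can say only that no measure is specified in the visible text, since the questionnaire, information sheet and consent script cannot be seen.
- *The protocol itself names disclosure as a harm of the intervention.* Section 2.3.1 names it as the reason for waiving parental consent. The link to delivery and calls is inferred, though participants may be as young as 16 and the inference is modest.
- *The DSMB works from the wrong list of harms.* Nothing confines it to what 2.5 lists.
- *The comparison of harms between arms is distorted.* No such comparison is planned. Section 2.3.1 also has field staff reconfirm consent at every follow-up round, apparently in both arms, and the Zalo and telephone channels are open to all. Reporting may differ by arm; that it does is not shown.
- *The wrong label caused the capture gap.* The two occur together, but the documents do not connect them.

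It is also fair to say that the illustration's rates come from nowhere in the documents, and that a retained man may still decline a harm question. The 92% and 87% are therefore upper values for the assumed 5% risk.

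**Conclusion.** The concern holds in limited form. Three things are established from the text: section 2.5 gives a design label that contradicts the rest of the protocol and the SAP; it discusses no risk from couriered kits, video sessions or study contact; and, mental health apart, no harm measure is specified, with capture left to events that come to notice. Sections 2.5 and 2.6 also disagree on identifiers.

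Correcting the label alone would be close to clerical. The useful change is to ask about harms directly, which is inexpensive and bears on participant safety. Its size cannot be stated from the documents. Under an assumed 5% risk in 50 men, the chance of at least one report is 92% if all are asked and answer, against 22% to 72% if 10% to 50% of events are volunteered. None of the primary or secondary effectiveness analyses is affected.

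**What to change.** - In protocol section 2.5, describe the study as the pilot randomised trial that sections 2 and 2.1.1 set out. List unintended disclosure through kit delivery, messages or calls as a study risk beside the questionnaire items.
- Reconcile the statement in 2.5 that no identifying information is recorded with the matching by nickname and phone number in 2.6.
- Add the same few items to the remaining 6- and 12-month Qualtrics surveys in both arms: unwanted disclosure linked to the study, pressure to test or to show a result, and mistreatment after testing or contact. Make them optional. Section 2.5 lets participants skip any question, whereas 2.6 makes key items mandatory, so the new items should be set explicitly as non-mandatory.
- Route positive answers into the section 2.7 incident process. Report counts by arm, with the number of men asked and the number answering, to the DSMB and in the results.

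The cost is a wording amendment, a slightly longer survey and more incidents to review. Coverage will be incomplete if some follow-up has already taken place. That is possible, since section 4 reports three DSMB meetings as held and section 2.3.2 describes discontinuation in the past tense. In that case the results should say which men were never asked.
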